1.2. STUDY TITLE

Observational Study Describing Treatment Convenience in Patients Treated With Dabigatran for Stroke Prophylaxis in Non-Valvular Atrial Fibrillation.

1.3. PROTOCOL CODE

BI 1160.253

1.4. COORDINATING INVESTIGATORS

1.5. TYPE OF SITES WHERE THE STUDY IS BEING CONDUCTED

The study is being conducted at approximately 200 cardiology centres and non-specialist centres where Pradaxa® and VKAs are regularly prescribed for stroke prophylaxis in NVAf,

under regular medical practice conditions and in accordance with daily clinical practice. These centres are located in four Autonomous Communities.

1.7. PRIMARY OBJECTIVE

The primary objective of this study is to describe patients' perception of their treatment for NVAf using the PACT-Q2 questionnaire at three time points: during the baseline period (after the indication for Pradaxa®), after approximately one month and during the continuation period.

1.8. STUDY DESIGN

National, multi-centre, observational study based only on obtaining new data. The study will enrol patients in Spain with NVAf who are treated with VKAs and subsequently start Pradaxa®, and who have given their consent.

Patients will be monitored for a period of six months. Data will be collected at three time points:

1. After the indication for Pradaxa® (baseline period)
2. 30-45 days after starting treatment with Pradaxa® (initial period)
3. 150-210 days after starting treatment with Pradaxa® (continuation period)

The visit windows above for Visit 2 and Visit 3 should be seen as guidance for the treating physician. Visit schedule deviations are expected as the visits are being scheduled according to local clinical routine. For analysis purpose, Visit 2 data that were collected between 7 and 124 days after initiation will be included (rationale for the lower limit is that steady state on Pradaxa® is achieved after 3 days, and first side effects also might occur after a 1st or 2nd intake; rationale for the higher limit is to make sure that there is no overlap with Visit 3). Visit

3 data that were collected between 125 and 365 days after initiation will be included for analysis.

Due to Pradaxa® initiation date was not recorded in the eCRF, it is assumed that the initiation date of Pradaxa® is the day after the VKA end date.

1.9. DISEASE OR DISORDER UNDER STUDY

Non-valvular atrial fibrillation with a risk of stroke.

1.10. INFORMATION ON THE STUDY MEDICATION

- Pradaxa® 110 mg hard capsules
- Pradaxa® 150 mg hard capsules

Pradaxa® 110 mg and Pradaxa® 150 mg hard capsules contain dabigatran etexilate (active substance: dabigatran).

Patients will receive a single daily dose of Pradaxa® in accordance with the product's Summary of Product Characteristics, the Therapeutic Positioning Report issued by the competent authorities in Spain and the authorisations of the various autonomous communities.

The current version of the Summary of Product Characteristics (SmPC) for Pradaxa® can be found on the EMA's website.

The following link is updated with the most recent authorised version of the SmPC:

<http://ec.europa.eu/health/documents/community-register/html/h442.htm>

1.11. STUDY POPULATION AND TOTAL NUMBER OF SUBJECTS

The study population is made up of patients with a diagnosis of NVAf who are suitable for transfer from treatment with VKAs to treatment with Pradaxa®, in accordance with the Summary of Product Characteristics for Pradaxa®. Patients will be enrolled in the study following the decision to start treatment with Pradaxa®. The decision to start treatment with Pradaxa® is based on the recommendations of the health authorities described in the therapeutic positioning report for NOACs.

The planned enrolment is a total of 1087 patients from cardiology centres and non-specialist centres that regularly prescribe Pradaxa® and VKAs for stroke prophylaxis in NVAF in accordance with the recommendations of the health authorities described in the therapeutic positioning report for NOACs.

1.12. STUDY SCHEDULE

The estimated key dates are:

- Start of data collection: June 2016
- End of data collection: July 2018
- Final study report: January 2019

1.13. SOURCE OF FUNDING

The sponsor, Boehringer Ingelheim España, S.A., will pay for all expenses that may arise from the study, including: logistics management, statistical analysis and investigators' fees. The sponsor issues a financial report for the study, which details the fees that will cover the costs of participation for the site and the investigators.

Because the study is being conducted under the normal conditions of clinical practice, and because the patients will not undergo any diagnostic or follow-up procedure that is not a part of routine clinical practice, the study does not involve extraordinary expenses for the investigator or site other than the investigator's commitment to complete the required information on the electronic case report form designed for this purpose.

2. GLOSSARY OF ABBREVIATIONS

The meanings of the abbreviations used in this document are explained below:

AE:	Adverse Event
SAE	Serious Adverse Event
DOAC	Direct oral anticoagulant
AST/ALT	Aspartate aminotransferase/Alanine aminotransferase
VKA	Vitamin K antagonist
B	Beta
DB	Database
AC	Autonomous Community
IEC	Independent Ethics Committee
CRF	Case Report Form
eCRF	Electronic case report form
SD	Standard deviation
ECG	Electrocardiogram
EMA	European Medicines Agency
NVAF	Non-valvular atrial fibrillation
HR	Heart rate
ICH	Intracranial haemorrhage
CI	Confidence interval
BMI	Body mass index
INR	International Normalised Ratio
MedDRA	Medical Dictionary for Regulatory Activities
Min	Minimum
Max	Maximum
n	Number of cases

p	p-value associated with the statistical test used
DBP	Diastolic Blood Pressure
SAP	Statistical analysis plan
SBP	Systolic Blood Pressure
DMP	Data management plan
AR	Adverse reaction
SAS	Statistical Analysis System
ACS	Acute Coronary Syndrome
ACS-STEMI	Acute Coronary Syndrome. ST-segment elevation myocardial infarction
ACS-NSTEMI	Acute Coronary Syndrome. Non-ST-segment elevation myocardial infarction
SmPC	Summary of Product Characteristics
CNS	Central Nervous System

3. STUDY OBJECTIVES

3.1. PRIMARY OBJECTIVE

The primary objective of this study is to describe patients' perception of their treatment for NVAf using the PACT-Q2 questionnaire at three time points: during the baseline period after the indication for Pradaxa[®], after approximately one month and during the continuation period:

- Visit 1 or baseline visit: when the patient is receiving treatment with VKAs for the prophylaxis of stroke/embolism and has changed treatment (baseline period to record the perception of treatment with VKAs). Patients will be enrolled in the study following the decision to start treatment with Pradaxa[®]. The decision to start treatment with Pradaxa[®] is based on the recommendations of the health authorities described in the therapeutic positioning report for NOACs.
- Visit 2 or initial period: when treatment with Pradaxa[®] has commenced (30-45 days).
- Visit 3 or continuation period: when continuing treatment with Pradaxa[®] (~180 days).

As indicated in section 1.8, Visit 2 data that were collected between 7 and 124 days after baseline will be included for analysis; Visit 3 data that were collected between 125 and 365 days after baseline will be included for analysis.

3.2. SECONDARY OBJECTIVES

Characterisation of the patient population in Spain:

- Demographic data (age, sex, comorbidities and concomitant medication)
- Obtaining elements assessed by the physician to calculate the HAS-BLED score during the baseline period.
- Obtaining elements assessed by the physician to calculate the CHA₂DS₂-VAsC score during the baseline period.
- If available: analytical evaluation of kidney function and calculation of creatinine clearance using the Cockcroft-Gault formula.
- Initial Pradaxa[®] dose
- Reasons for changing the dose of Pradaxa[®] or discontinuing Pradaxa[®]/VKAs.

4. STUDY POPULATION

4.1. SELECTION CRITERIA

Patients who meet all the inclusion criteria and none of the exclusion criteria indicated below are considered eligible to take part in the study.

4.1.1. Inclusion criteria

1. Granting informed consent in writing prior to enrolment
2. Patients of both sexes ≥ 18 years of age with a diagnosis of NVAF.
3. Patients treated continuously with VKAs for stroke prophylaxis for at least six months prior to the baseline visit.
4. Patients switching to treatment with Pradaxa® in accordance with the recommendations of the competent health authorities described in the therapeutic positioning report for NOACs and the authorisations of the various autonomous communities.

4.1.2. Exclusion criteria

1. Contraindications for the use of Pradaxa® or VKAs described in the Summary of Product Characteristics (SmPC).
2. Patients receiving Pradaxa® or VKAs for any reason other than stroke prophylaxis in NVAF.
3. Participation in any clinical trial of an investigational medicinal product or medical device.

4.2. JUSTIFICATION FOR SAMPLE SIZE

The prospective collection is planned of data from approximately 1087 patients by approximately 200 principal investigators at cardiology and internal medicine centres and non-specialist centres that regularly prescribe dabigatran and VKAs for stroke prophylaxis in NVAF in accordance with the recommendations of the health authorities described in the therapeutic positioning report for direct oral anticoagulants (DOACs).

The participating centres are located in the autonomous communities of Catalonia, Galicia, Andalusia and the Basque Country.

As is established in the study protocol, due to the limited number of publications on the PACT-Q questionnaire (see reference studies in the Bibliography section of the protocol) and the absence of information on the clinical significance of variations in the PACT-Q scale, the sample size has been calculated using standardised mean differences. Specifically, in the context of this study, these represent the mean differences in the PACT-Q questionnaire score obtained at two different time points, divided by the corresponding standard deviations. Generally, a standardised effect size of 0.2 is considered to represent a small change, 0.5 represents a moderate change and 0.8 a large change.

Assuming a two-sided alpha level of 0.05 and a 20% loss to follow-up, a sample size of 1087 patients will give a statistical power of 90% for the detection of a standardised mean difference of 0.11 for the primary endpoint, the evaluation of PACT-Q2 questionnaire scores obtained during the final and baseline assessments.

5. METHODS

5.1. DATA PROCESSING

The data will be collected by each investigator through an electronic case report form (eCRF). All the data from the eCRFs will be entered into a database created for this purpose and set up with ranges and rules for internal consistency, to ensure quality control of the data.

5.1.1. Database

A computerised database will be created in which the data obtained during the study will be verified. Once the database has been debugged, the statistical analysis will be performed.

5.1.2. Database debugging

The data will be debugged before the clinical DB is closed. In section 8.1 details will be provided of this process, both those specified and agreed upon in the study's Data Management Plan and the statistical debugging performed during the analysis.

5.2. DATA ANALYSIS AND STATISTICAL TESTS

5.2.1. Changes in the planned analysis

The SAP version 1.0 of 2nd February 2018 has been modified, according an express request of the sponsor.

The following sections have been modified:

- Section 1.8, Study Design: the valid visit windows between initiation date of Pradaxa® and Visit 2 / Visit 3 have been defined
- Section 1.12, Study schedule: the dates have been modified according the real dates
- Section 3.1, Primary Objective: the valid visit windows between initiation date of Pradaxa® and Visit 2 / Visit 3 have been defined
-
- Section 5.2.7, Statistical methodology: an explanatory note about the exploratory purposes of the analysis has been added.
- Section 6.1, Study population:
 - The valid VKA end date have been defined in inclusion criterion 4
 - The need of having the PACT-Q2 in all the study visits has been deleted
- Section 6.2.1 and 6.2.2, Socio-demographic data and Anthropometric data and vital signs: the p-value between males and females has been deleted in Table 2, Table 4 and Table 5.
- Section 6.2.1, Socio-demographic data: a categorisation about age (≤ 65 or > 65 years) has been added in Table 2.
- Section 6.2.6, Scales: the number of section 6.2.6.3 has been updated.
- Section 6.2.6.3, PACT-Q2 Questionnaire at Baseline: the title of the section and the title of Table 15, Table 16 and Table 17 have been changed, adding “at Baseline”.
- Section 6.3.1, Treatment with Pradaxa®: the header cells have been changed, deleting the specification of the period days in each visit.
- Section 6.3.2.1, PACT-Q2 Questionnaire at Follow-up: the title of the section has been changed, adding “at Follow-up”.
- Section 0, Analysis of the Secondary endpoints:
 - A categorisation about age (≤ 65 or > 65 years) has been added in Table 26.
 - The reference to the Thromboembolic risk (CHA2DS2-VASc) section has been updated in Table 26.
-

- Section 8.2, Reasons for Discontinuing Pradaxa®: the header cells have been changed, deleting the specification of the period days in each visit.

5.2.2. Samples for analysis

The analyses will be performed on a single sample of assessable patients (eligible patients terminology is used in the Study Protocol), which will include all patients who meet the selection criteria.

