5.2.3. Analysis of the primary endpoint

The description of patients' perception of their treatment for NVAf will be achieved using the PACT-Q2 questionnaire.

For this, comparisons of paired samples (Student's paired t-test or the non-parametric Wilcoxon signed-rank test for data without a normal distribution) will be used to compare the scores obtained in the final assessment (continuation period) to those from the baseline assessment. Additional comparisons will be performed on the scores obtained in the intermediate assessment (initial period) in comparison to the baseline assessment, and the scores obtained in the final assessment in comparison to the intermediate assessment.

For the analysis of the primary endpoint, the instructions described below will be followed:

- Patients with a VKA end date before V1 date: patients who had the Pradaxa® initiation date (the date after VKA end date) within 7 days before V1 date, will be included in the corresponding analyses V1 vs V2 and/or V1 vs V3 and/or V2 vs V3, provided the new visit windows for V2 and/or V3 are met*.
- Patients with Pradaxa® initiation date (the date after VKA end date) = V1 date: all patients will be included in the corresponding analyses (V1 vs V2 and/or V1 vs V3 and/or V2 vs V3), provided the new visit windows for V2 and/or V3 are met*
- Patients with Pradaxa® initiation date (the date after VKA end date) after V1 date: all patients will be included in the corresponding analyses (V1 vs V2 and/or V1 vs V3 and/or V2 vs V3), provided the new visit windows for V2 and/or V3 are met*

* The acceptance windows days for visit 2 and visit 3 will be the following:

- V2 date - Day after VKA end date= 7-124 days
- V3 date - Day after VKA end date= 125-365 days

(NOTE: Due to Pradaxa® initiation date was not recorded in the eCRF, it is assumed that the initiation date of Pradaxa® is the day after the VKA end date)

These analyses will be performed based on the actual anticoagulant treatment received by the patients (i.e. “as-treated” analysis), so that patients who discontinue the initial anticoagulant treatment at the time of an assessment will be excluded from all analyses where data from that assessment is included.

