D2. Do you think that the anticoagulant treatment you are taking has been able to reduce your symptoms (pain or swelling in the legs, palpitations, shortness of breath, chest pain, etc.)?					
	They are much worse than I expected	They are worse than I expected	They are about what I expected	They are better than I expected	They are much better than I expected
D3. How do the side effects you have, such as small bruises or bleeding (when shaving, cooking, if you cut yourself, etc.) compare to what you expected?					

Table 16. PACT-Q2 Questionnaire at Baseline (II)

SATISFACTION WITH THE ANTICOAGULANT TREATMENT	n (%)	n (%)	n (%)	n (%)	n (%)
	Very unsatisfactory	Unsatisfactory	Neither satisfactory nor unsatisfactory	Satisfactory	Very satisfactory
D4. With regard to the follow-up of your disease and the anticoagulant treatment you are taking, what is your degree of satisfaction with your level of independence?					
D5. What is your degree of satisfaction with the methods (appointments with nurses, doctors, laboratories, etc.) used to ensure the follow-up of your disease and anticoagulant treatment?					
D6. What is your degree of satisfaction with the presentation of your anticoagulant treatment (pill to be taken orally/injections)?					
D7. In general, what is your degree of satisfactions with your anticoagulant treatment?					

The PACT-Q2 questionnaire is made up of two domains:

- Convenience (items B1 to B7 and C1 to C2) → This domain is calculated by adding the inverted scores (6 – item score) for each of the 9 items in question, and converting to a scale from 0 to 100.
- Satisfaction with the anticoagulant treatment (items D1 to D7) → This domain is calculated by adding the scores for each of the 7 items in question, and converting to a scale from 0 to 100.

The table below will describe the scores obtained for both domains:

Table 17. PACT-Q2 Questionnaire Score at Baseline¹
DOMAINS
Convenience Mean (SD) 95% CI Median (P25; P75) (Min; Max) Valid N
Satisfaction with the anticoagulant treatment Mean (SD) 95% CI Median (P25; P75) (Min; Max) Valid N

¹ Range from 0 to 100

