D6. What is your degree of satisfaction with the presentation of your anticoagulant treatment (pill to be taken orally/injections)?					
D7. In general, what is your degree of satisfactions with your anticoagulant treatment?					

The table below will describe the scores obtained in the 2 domains of the PACT-Q2 questionnaire at both time points during follow-up:

Table 24. PACT-Q2 questionnaire score¹ during follow-up		
DOMAINS	Visit 2	Visit 3
Convenience		
Mean (SD)		
95% CI		
Median (P25; P75)		
(Min; Max)		
Valid N		
Satisfaction with the anticoagulant treatment		
Mean (SD)		
95% CI		
Median (P25; P75)		
(Min; Max)		
Valid N		

¹ Range from 0 to 100

6.4. ANALYSIS OF THE PRIMARY ENDPOINT: PERCEPTION OF TREATMENT FOR NVAF USING THE PACT-Q2 QUESTIONNAIRE

This section will analyse the primary objective of the study, which is to describe patients' perception of their treatment for NVAF using the PACT-Q2 questionnaire at three time points: during the baseline period after the indication for Pradaxa®, after approximately one month and during the continuation period.

For the analysis of the primary endpoint, the instructions described in section 5.2.3 will be followed.

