6.4.1. PACT-Q2 questionnaire scores during follow-up

Table 25. Evolution of PACT-Q2 questionnaire scores				
DOMAINS	Visit 1	Visit 2	Visit 3	p¹
COMPARISONS for VISIT 1 vs VISIT 2				
Convenience (range from 0 to 100)				
Mean (SD)		--		
95% CI		--		
Median (P25; P75)		--		
(Min; Max)		--		
Valid N		--		
Satisfaction with anticoagulant treatment (range from 0 to 100)				
Mean (SD)		--		
95% CI		--		
Median (P25; P75)		--		
(Min; Max)		--		
Valid N		--		
COMPARISONS for VISIT 1 vs VISIT 3				
Convenience (range from 0 to 100)				
Mean (SD)			--	
95% CI			--	
Median (P25; P75)			--	
(Min; Max)			--	
Valid N			--	
Satisfaction with anticoagulant treatment (range from 0 to 100)				
Mean (SD)			--	

Table 25. Evolution of PACT-Q2 questionnaire scores				
DOMAINS	Visit 1	Visit 2	Visit 3	p¹
95% CI			--	
Median (P25; P75)			--	
(Min; Max)			--	
Valid N			--	
COMPARISONS for VISIT 2 vs VISIT 3				
Convenience (range from 0 to 100)				
Mean (SD)	--			
95% CI	--			
Median (P25; P75)	--			
(Min; Max)	--			
Valid N	--			
Satisfaction with anticoagulant treatment (range from 0 to 100)				
Mean (SD)	--			
95% CI	--			
Median (P25; P75)	--			
(Min; Max)	--			
Valid N	--			

¹ Student's t-test or Wilcoxon test

NOTE: Patients without dates in range in each visit, will be excluded of the comparisons involved

Figure 6. Evolution of PACT-Q2 questionnaire scores
(Line graph for the 2 domains at the 3 study time points)

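### Tables 15-17 carry no Visit 1 timing limit, so answers given more than 7 days into Pradaxa can be tabulated as baseline (VKA) perception

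*SAP*

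**What the plan says.** Section 3.1 gives the purpose of Visit 1: "baseline period to record the perception of treatment with VKAs". Section 5.2.2 sets one analysis sample: "The analyses will be performed on a single sample of assessable patients", "which will include all patients who meet the selection criteria". Section 6.1.1 describes how those criteria are verified. For criterion 3 it removes patients without VKA start and end dates and patients with less than six months of treatment. For criterion 4 it says that adherence to the positioning report cannot be assessed from the eCRF. Neither check compares the VKA end date with the Visit 1 date.

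The Pradaxa start date was not recorded, so 1.8 and 5.2.3 take it to be the day after VKA end. For patients whose VKA ended before Visit 1, 5.2.3 says: "patients who had the Pradaxa® initiation date (the date after VKA end date) within 7 days before V1 date, will be included". This inclusion is into the V1-V2, V1-V3 and V2-V3 analyses. Section 6.4 takes up the rule: "For the analysis of the primary endpoint, the instructions described in section 5.2.3 will be followed". The footnote to Table 25 reads: "NOTE: Patients without dates in range in each visit, will be excluded of the comparisons involved". Section 6.2.6.3, which contains Tables 15-17, has no timing condition; before Table 17 it says only: "The table below will describe the scores obtained for both domains".

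**The concern.** The SAP recognises that some patients had stopped VKA before Visit 1, and it treats more than 7 days of assumed Pradaxa use as too long for a Visit 1 score to enter the comparisons. It does not carry that standard to the tables that describe Visit 1. A patient who stopped VKA 30 or 60 days before Visit 1 passes the 6.1.1 check if the dates are present and treatment lasted six months. That patient's Visit 1 answers then appear in Tables 15-17 under the baseline label.

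The primary objective is itself descriptive: perception at three time points. Tables 15 and 16 are the only place where baseline perception is shown item by item. If Pradaxa-period answers are mixed in, the description of the VKA period is pulled towards the follow-up scores, and the table gives the reader no sign of it.

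**Working it through.** **1. The plan's own figure.** Inputs from 4.2: two-sided alpha 0.05, power 90%, standardised mean difference 0.11, 20% loss.

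n = ((1.960 + 1.282) / 0.11)² = 868.4, rounded up to 869 completers. 869 / 0.80 = 1086.25, rounded up to 1087. The stated sample size reproduces. The point does not depend on it; 1087 is used below only as a scale.

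**2. Which rule reaches which table.**

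| Output | Sample rule that applies | Limit on time on Pradaxa at Visit 1 |
|---|---|---|
| Tables 15-17 (6.2.6.3) | 5.2.2 with the 6.1.1 checks | none |
| Table 25 (6.4.1) | 5.2.3, through 6.4 | at most 7 days |
| Figure 6 (6.4.1) | sample not stated | unclear |

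Section 1.8 sets analysis windows for Visit 2 (7-124 days after initiation) and Visit 3 (125-365 days), but none for Visit 1. On the SAP's own clock, a Visit 1 questionnaire completed 30 days after the assumed start falls at a time that would qualify as Visit 2 data.

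**3. Size of the shift.** Let p be the share of patients in Table 17 who had been on Pradaxa for more than 7 days at Visit 1, and d the difference between their mean score and the VKA mean, in SD units. The tabulated mean is (1 - p) × VKA mean + p × (VKA mean + d), so the shift is p × d.

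The SAP does not give p; 5-20% is an assumption. For d, two reference values come from 4.2: 0.11 (the planned detectable difference) and 0.5 (described there as moderate).

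| Assumed p | Patients out of 1087 | Shift at d = 0.11 | Shift at d = 0.5 |
|---|---|---|---|
| 5% | 54 | 0.006 SD | 0.025 SD |
| 10% | 109 | 0.011 SD | 0.050 SD |
| 20% | 217 | 0.022 SD | 0.100 SD |

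**4. Comparison with sampling error.** The 95% CI half-width for a mean at N = 1087 is 1.96 / √1087 = 0.059 SD. The shift exceeds it when p > 0.059 / 0.5, about 12%, at d = 0.5, or when p > 0.059 / 0.11, about 54%, at d = 0.11. Most of the assumed range therefore lies inside the reported interval. Unlike sampling error, however, the shift does not shrink as N grows.

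This comparison treats the SD in 4.2 and the SD of a single-visit score as the same scale. The 0.11 relates to paired differences, and the two SDs coincide only if the correlation between visits is 0.5. The figures show order of magnitude only.

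**The case against.** The strongest reply is that criterion 3, as worded in 4.1.1, asks for continuous VKA treatment over the six months before the baseline visit, and Table 1 lists failure of this as a reason for being non-assessable. On that reading a patient 30 days off VKA never reaches Tables 15-17. But 6.1.1 does not check the criterion in that way. The first bullet of 5.2.3 would also need no 7-day limit if patients with longer gaps had already been removed. The reply does show that the wording admits two readings, and that either 6.1.1 or 6.2.6.3 has to settle it.

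A related reply is that the change list in 5.2.1 mentions a valid VKA end date under criterion 4. The list is not the operative text, and a mismatch with it is not the point here. It suggests that a limit on the assessable sample may have been intended. The 6.1.1 text available for review contains none; if one exists elsewhere, Tables 15-17 would inherit it.

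The as-treated clause of 5.2.3 does not help, because it governs the primary-endpoint analyses only.

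Several counterpoints stand in full. Table 25 gives restricted Visit 1 summaries for both domains, so only the item frequencies lack a restricted counterpart. Section 5.2.7 calls all analyses descriptive and exploratory, and no test uses Tables 15-17. Section 5.2.3 bars longer gaps by implication, not by an explicit exclusion. The PACT-Q2 items ask about the patient's anticoagulant treatment in the present tense, but that a switched patient answers about Pradaxa is an inference.

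**Conclusion.** The point holds for Tables 15-17. As 6.1.1 puts the criteria into practice, the assessable sample has no limit on the gap from VKA end to Visit 1, and the 5.2.3 limit stops at the primary comparisons. The baseline PACT-Q2 tables can therefore include Pradaxa-period answers, against the purpose stated in 3.1. Figure 6 has the same weakness at Visit 1 if it is drawn from the full sample.

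The size cannot be fixed from the SAP. It rests on an assumed share of 5-20% and on answers at Visit 1 already reflecting Pradaxa. It could be negligible, or as large as 0.10 SD.

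A reader might infer three stronger things that the SAP does not support:

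- **That the primary comparisons are contaminated by these patients.** They are not: 5.2.3 keeps longer gaps out of Table 25.
- **That this gap explains any disagreement between Tables 17 and 25 at Visit 1.** The two will differ in any case, because Table 25 uses paired patients with follow-up visits in window, as its footnote and valid N indicate.
- **That the baseline means are shown to lie outside their error bars.** At a 0.5 SD difference that needs a share above about 12%, and the share is unknown.

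**What to change.** In 6.2.6.3, state that Tables 15-17 include Visit 1 scores only from patients whose assumed Pradaxa start is not more than 7 days before Visit 1, as in 5.2.3, and report the number set aside. Say which sample supplies the Visit 1 point of Figure 6, and apply the same limit if it is the full sample.

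Alternatively, put the limit into the 6.1.1 check of criterion 3, so that every table inherits it and Table 1 counts the patients removed. The choice is whether such patients should leave only the baseline PACT-Q2 tables or the assessable sample as a whole; the SAP should state which.

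The cost is one sentence and a filter on dates already derived for Table 25. The baseline PACT-Q2 tables lose a little N. Patients up to 7 days on Pradaxa would remain, as they do in Table 25, so the change aligns the tables without making Visit 1 a pure VKA measurement. Tables 17 and 25 will still not match exactly, and a footnote should say so.
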